### Eligibility Criteria

The anticipated initial user population for the Pivot Breath Sensor System are lay users who are smokers, ages 18-80, and capable of using a smartphone to download the Sensor-Only app. The intended users range in age, degree of smoking, mental and physical capabilities, health literacy, experience using other CO analyzers or home use medical devices, and experience using smartphones.

Study participants will consist of individuals who represent the intended user profile, current smokers. Participant criteria include all of the following:

#### Inclusion Criteria

- 18-80 years of age
- Current daily cigarette smokers (at least 10 cigarettes per day)
- Resident of the United States
- Able to read and comprehend English
- Owns and uses a smartphone compatible with the study app (iPhone 5 and above, operating system iOS 11 and above, or, Android 5.0 and above, operating system Android 5.0 and above)
- Willing to sign the Informed Consent Form

#### Exclusion Criteria

- Pregnancy
- Participation in a previous study sponsored by Carrot Inc.

The study will employ non-proportional quota sampling as follows to ensure the study population mirrors the expected initial intended user population:

Age	18-29 years ≤ 20 % of sample	30-60 years Remainder	61-80 years ≤ 10 % of sample
Stage of Change*	Quit 30 days ≥ 20% of sample	Quit 6 months ≥ 20% of sample	Not interested < 20 % of sample
Gender	Male 40-60%	Female 40-60%	
Cigarettes Per Day (CPD)	10-19 CPD 40-60%	≥ 20 CPD 40-60%	
Employment**	Unemployed 4-8% of sample	Employed Remainder	

- \*Stage of Change question and answer choices: Are you seriously thinking of quitting smoking? A. Yes, within the next 30 days B. Yes, within the next 6 months C. No, not thinking of quitting
- \*\* Employment rate among study participants is sought to align with employment rates among the general US population, which currently is 3.7% (Bureau of Labor Statistics, U.S. Department of Labor. The Employment Situation – July 2019. USDL-19-1388. Released August 2, 2019. <https://www.bls.gov/news.release/pdf/empsit.pdf>)

#### 6.4 SUBJECT RECRUITMENT, INFORMED CONSENT AND ENROLLMENT

Subjects will be recruited in the United States through web media (e.g. Facebook, Google Ads) [REDACTED] and/or via a clinical recruiter. Potential participants will be asked to provide contact information (phone number, email address), and answer questions on demographics (gender, age, employment status, location via city and state), smartphone ownership and smoking behavior using the Online Screening Form [REDACTED] or through the clinical research recruiter, if applicable. Study staff will review each potential participant's responses to the eligibility questions. Potential subjects may also convey their interest in participating in the study by responding to outreach from the clinical recruiter.

All study participants will undergo a screening phone call where they will be asked questions to confirm study eligibility [REDACTED]. Potential participants will be called on a first-come-first-served basis with nonproportional quota sampling enrollment guidelines applied. During this call, study personnel will inform the potential participant of the study details and will answer any questions. Eligible participants who meet the inclusion/exclusion criteria will be offered the opportunity to participate in the study.

Potential subjects will then determine if they would like to proceed with registration, and if so, study personnel will email the potential subject an electronic Informed Consent Form [REDACTED]. The potential subject will have ample time to read the Informed Consent Form (ICF) and the opportunity to ask questions. The subject will sign the

electronic ICF before participating in this study. Once signing the ICF, the subject will be given a unique identifier to protect subject privacy. Participation in this research is voluntary. Participants may discontinue participation at any time without penalty or loss of benefits to which they are otherwise entitled. Participants may choose to exit the study at any time. They are not required to complete the study if they choose to stop.

Participants will be considered enrolled after completing the following 4 tasks: electronically signing the informed consent form, pairing their breath sensor to the Sensor-Only app on their smartphone, giving their first breath sample, and completing the Baseline Questionnaire.

## **6.5 SUBJECT STIPEND**

Participants are compensated for doing breath samples (up to \$220), completing the online questionnaires (up to \$220 in total for 7 questionnaires) and for returning the Pivot Breath Sensor (\$50). Participants will be compensated up to \$490 in total. Compensation will be in the form of Visa gift cards that are mailed to their provided address. Payments will be bundled as depicted in the Informed Consent Form with participants receiving up to 5 payments over the course of the study. Bundled payments will be processed upon completion of the item(s) for which the participant is receiving payment and will take 2-3 weeks to arrive to the participant after being ordered.

## **6.6 SAMPLE SIZE AND JUSTIFICATION**

This study will enroll up to 220 participants. Consideration for the sample size included powering the study to observe a clinically meaningful change from baseline for the primary and secondary endpoints using 80% power at a statistical significance of  $P < 0.05$ . The primary endpoint utilized preliminary data from a similar 37 participant pilot study. Data at the 14-day time point showed 31%, 66% and 3% of participants had increased, unchanged and decreased Stage of Change, respectively, from baseline. To detect a statistically significant change in these proportions requires enrolling 50 participants.

The estimated proportion of participants achieving  $\geq 1$  quit attempt is 25% based on interim results from the pilot study. Based on the median prevalence of 65.4% for past-year quit attempts in the general population [13], the average monthly quit attempt rate is approximately 5%. To show that a proportion of 25% of participants making a quit attempt by day 28 is statistically different from 5% will require  $n=16$ .

Finally, literature indicates approximately 1% of the general population [14-18] and 2-5% of individuals in cigarette reduction studies [19, 20] will reduce their CPD by  $\geq 50\%$  on a monthly basis. Assuming that 10% of participants in the present study reduce their CPD by  $\geq 50\%$  by day 28, the present study will require  $n=185$  to show a difference from 5%. Taking these analyses into consideration along with expected attrition, the present study will enroll up to 220 participants.

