## 8. DATA COLLECTION

Study personnel will collect information from the participant over the course of the study including:

- Age
- Gender
- Pregnancy status (self-reported) in women
- Race/ethnicity
- Type of smartphone participant used (iPhone or Android)
- Number of years smoking
- Quit attempts
  - Past 12 months
  - During the study
- Number of cigarettes currently smoked per day (CPD)
- 7-day point prevalence abstinence (PPA)
- 30-day point prevalence abstinence (PPA)
- Use of any combustible, inhaled tobacco product other than cigarettes (pipes, cigars, cigarillos, etc.), any electronic cigarette product (e-cigs, vape, vapor), and any other inhaled combustible material
- Use of smoking cessation medications
- Participation in a smoking cessation program
  - Past
  - Present
- Ability to access settings (sensor battery life reading and “Sync Now” function) in the Sensor-Only app
- Attitudes towards smoking
  - Desire to quit (y/n)
  - Stage of Change
  - Readiness to quit (scale 1-10)
  - Confidence to quit (scale 1-10)
  - Perceived difficulty of staying quit (scale 1-10)
  - Goals
- Feedback on breath sensor set-up
  - Ease/difficulty getting started with the breath sensor (scale 1-5)
  - Ease/difficulty following directions on the breath sensor screen (scale 1-5)
  - Ease/difficulty of to understand error messages on breath sensor screen if applicable (scale 1-5)
- Feedback on breath sensor experience and use
  - How would you improve the Pivot Breath Sensor experience?
  - Please describe any issues you’ve had with the breath sensor
  - How likely are you to recommend the Pivot Breath Sensor to a friend/colleague? (scale 1-10)
  - Do you use the breath sensor at least once a day (if not, why?)
  - Are you using the breath sensor as often as you did in the beginning of the program? (if not, why?)

- Which of the following best describes your thoughts on the Pivot Breath Sensor? ('nothing else can help me with smoking' to 'it will not help me with smoking')
- Feedback on impact of breath sensor
  - Comprehension of CO and CO values as they relate to smoking behavior
  - How has seeing your CO values impacted you as it relates to:
    - your feelings?
    - learning?
    - your thoughts about smoking and daily smoking behavior?
    - your thoughts about quitting?
  - How has the breath sensor affected your motivation to quit smoking? (increase, no change, decrease)

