## 10.2 ANALYSIS

Changes in measurements from baseline will be assessed at different timepoints in the study. Participants will serve as their own controls and comparisons will be made to no change. One sample t-test will be used for numerical data. Fisher's Exact or Chi square tests will be used for categorical data. Analyses will be conducted to calculate mean (SD) for normally distributed variables for actual data or mean (SE) for modeled data and median (interquartile range) values in instances of non-normally distributed variables.

McNemar test will be used for 2-category match-paired data. Cohen kappa statistic will be used for 3-category match-paired data. To evaluate changes in attitudes or cigarettes smoked per day over time, repeated measures linear mixed model analyses will be performed using a compound symmetric correlation matrix to model the repeated measures within subjects. To make specific comparisons across time, F statistics will be computed using the results from the model. Statistical significance is set at  $P < .05$ .

Analyses for the outcomes will be evaluated for only those who complete the survey (i.e. completer) and assessed to take into account missing data. To be included in any completer analysis the participant must provide a baseline response and the outcome response. For outcomes that are missing data, these will be assessed pending the data type.

For categorical data, the last response post-baseline will be carried forward for the day 28 analysis and the last response post-28 days will be carried forward for the day 84 assessment. If there is not any data to carry forward, the data will be considered unchanged from baseline. Numerical data will use linear mixed modeling.

All deviations from the study protocol will be identified, recorded and analyzed.

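### Section 6.6's 5% natural monthly quit-attempt rate is the arithmetic floor of its own 65.4% yearly figure; a constant-rate conversion gives about 8% per 28 days and n of about 27 to 31 instead of 16

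*Combined protocol and SAP*

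**What the plan says.** Section 6.6 (Sample Size and Justification) builds the quit-attempt calculation in three steps.

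- Source figure: "Based on the median prevalence of 65.4% for past-year quit attempts in the general population".
- Conversion: "the average monthly quit attempt rate is approximately 5" percent. The conversion is not shown.
- Sample size: the expected proportion with at least one "quit attempt is 25% based on interim results from the pilot study", and "To show that a proportion of 25% of participants making a quit attempt by day 28 is statistically different from 5% will require" n=16, "using 80% power at a statistical significance of" P<0.05.

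The same section gives n=185 for the endpoint of cutting cigarettes per day (CPD) by at least half, and an enrolment ceiling of 220.

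Three other places bear on the figure. Section 6.3 compares the Day 28 quit-attempt proportion with zero, and counts only attempts with at least one smoke-free day. The quota table in 6.3 sets "Not interested < 20 % of sample" for Stage of Change. Section 8 lists quit attempts for "Past 12 months" among the data collected, but section 10.2 specifies no comparison that uses them.

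**The concern.** A yearly prevalence of at least one attempt cannot be divided by 12 to give the average monthly share of people attempting, unless each attempter attempts in only one month. Anyone who tries in two or more months is counted once in the yearly figure but contributes to several monthly ones. The division therefore gives a minimum, and the plan presents it as the average.

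This matters because the study has no control arm. The 5% is the only figure in the plan for how many smokers would try to quit anyway within the Day 28 window. If it is too low, an ordinary level of quitting looks like an effect of the sensor, and the error favours the device.

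A second feature may push the same way. With fewer than 20% allowed to be uninterested in quitting, more than 80% of the sample must say they are seriously thinking of quitting within 30 days or 6 months, whereas 6.6 describes its source as the general population. The documents do not say how large this effect is.

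**Working it through.** **Inputs.** From 6.6: yearly prevalence 65.4%, benchmark 5%, expected 25%, power 80%, alpha 0.05, n=16 and n=185, enrolment up to 220. The documents do not state whether the test is one- or two-sided; two-sided reproduces the plan's figures.

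**1. Reproduce the plan's n.** One-sample proportion, normal approximation:

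n = [(1.960·√(p0(1−p0)) + 0.842·√(p1(1−p1))) / (p1−p0)]²

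- 25% vs 5%: [(0.4272 + 0.3644)/0.20]² = 15.7, so 16. This matches.
- 10% vs 5% (CPD endpoint): [(0.4272 + 0.2525)/0.05]² = 184.8, so 185. This matches.

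The formula is sound; only the 5% put into it is in question.

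**2. The floor.** The yearly share cannot exceed the sum of the period shares, so the average period share is at least:

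- per month: 65.4/12 = 5.45%
- per 28 days: 65.4 × 28/365 = 5.0%

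The plan's 5% sits on the 28-day floor and slightly below the monthly one.

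**3. Check in the other direction.** A constant 5% a month gives 1 − 0.95¹² = 46% a year. A constant 5% per 28 days gives 1 − 0.95^(365/28) = 49%. Neither approaches 65.4%.

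**4. Constant-rate conversion.**

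- per month: 1 − 0.346^(1/12) = 8.5%
- per 28 days: 1 − 0.346^(28/365) = 7.8%

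**5. Effect on n.** Same formula, 25% against the new benchmark:

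| Benchmark | n |
|---|---|
| 5% (plan) | 16 |
| 7.8% (28 days) | 27 |
| 8.5% (month) | 31 |

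Both are far below 185 and 220. With n=185, 80% power against 25% holds up to a benchmark of about 16.9%; with n=220, up to about 17.5%.

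**6. Effect on interpretation, if 5% were the test value.** Section 6.3 does not say this, so the step is conditional. An exact binomial test with upper tail at most 0.025 would reject 5% at 16 of 185 (8.6%) or 19 of 220 (8.6%). If the sensor did nothing and the natural 28-day rate were 7.8%, the chance of reaching that count is about 37% (n=185) or 36% (n=220) with complete data.

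**7. Missing data lower this.** Under 10.2, categorical data with nothing to carry forward count as unchanged. As an assumption, let 35 of 220 be missing and scored as no attempt. The expected observed rate is 7.8% × 185/220 = 6.6%, and the chance of at least 19 attempters falls to about 13 to 14%.

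**The case against.** The strongest objection is that the plan never tests against 5%. Section 6.3 names zero, and 10.2 speaks of comparison with no change, so the 5% affects only a sample size of 16 that does not set the enrolment. That stands. A reader might infer that the plan as written has a 36 to 37% false-positive rate on this endpoint; it does not, because those figures describe a test that the plan does not specify. Correcting 6.6 alone would leave the stated comparison with zero as it is. What survives is that zero makes no allowance for natural attempts at all, so 5% remains the only figure in the plan that gives an observed rate any context.

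Second, the pilot's 25% exceeds the converted benchmarks, and power for it is not in doubt. This also stands; only results of roughly 9 to 12% are open to misreading.

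Third, a reader might infer from the quotas that the source population was less motivated, or that participants in the 30-day category expect to try before Day 28 and so push the natural rate to 10% or more. The documents do not support either. They give no intent distribution for the source, the item asks about seriously thinking of quitting and not about expecting to try, and participants also differ in smoking at least 10 cigarettes a day, with unknown effect.

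Fourth, the floor presumes that the 65.4% source counts attempts as the study does. If it includes attempts shorter than one smoke-free day, the rate on the study's definition could be below 5%. The documents cannot settle this.

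Last, the constant-rate figure is itself a model. Repeat attempts clustered within one period pull it towards the floor. If some smokers never attempt, it rises: to 9.2% a month if 10% never do (an assumed share). It is a more defensible central value than the minimum, but not a measured rate.

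**Conclusion.** The concern holds as a point about a benchmark and how results will be read. On the plan's own 65.4%, 5% is a lower bound presented as an average. The constant-rate equivalent is 7.8% per 28 days or 8.5% a month, and the n that rests on the benchmark is about 27 to 31. This assumes that the source shares the study's quit-attempt definition and that attempts occur at a constant, common rate.

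Power and total enrolment are not at risk. Enrichment for intent to quit may raise the natural rate further, by an amount the documents do not give. The practical exposure is a modest Day 28 result being credited to the sensor. Confidence is high for the floor arithmetic and lower for any particular natural rate in this sample.

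**What to change.** In 6.6, replace 5% with about 8% per 28 days, show the conversion, state that 5% is the lower bound, restate n=16 as about 27 to 31, and say whether the 65.4% source uses the study's quit-attempt definition.

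In 6.3 and 10.2, add a comparison of the Day 28 proportion with an expected 28-day proportion derived from participants' own baseline answers on past-12-month attempts. Use the count if one is recorded; otherwise apply the constant-rate conversion. The expectation is estimated, so the method must allow for its uncertainty and not treat it as a fixed test value. Report it beside the 8% benchmark. Any split by baseline Stage of Change should be descriptive only: a category at its 20% minimum would hold about 44 of 220. The same edit should reconcile 6.3's comparison with zero and 6.6's non-zero benchmark.

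The cost is wording in three sections and one extra analysis, with no new data and no more participants. The drawbacks are a less favourable benchmark and error in recalling attempts over 12 months, which is a reason to show both comparisons.

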## 6.7 STUDY ARTICLES

Pivot Breath Sensor in representative packaging [REDACTED] that includes:

- Pivot Breath Sensor
- USB charging Cable
- Replaceable Mouthpiece
- Quick Start Guide [REDACTED]
- Sensor-Only App [REDACTED]
- Package Insert [REDACTED]

## 6.8 USER MANUAL AND TRAINING

The Pivot Breath Sensor was designed to be as intuitive as possible, such that users are able to understand how to use the product on their own. A Quick Start Guide, Package Insert, and package labeling is included with the device to aid the user and an online User Manual is also available. All of these items will be accessible to the study participant. A phone number will be included within the labeling material to contact customer support. In this study, users will be contacted via phone, email and/or text to check on the status of the device setup. Help will be offered if the user is having difficulty.

## 6.9 TEST ENVIRONMENT

The study will be performed remotely on an ambulatory basis. The device will be mailed to the participant's indicated address and the participant will use it throughout their day, going about life as they normally would.

## 6.10 STUDY PERSONNEL

The study team members will be trained by reading the study protocol. The study team members will have full training on the operation of the study devices and Sensor-Only app.

## 6.11 IRB OVERSIGHT

This study will be conducted under IRB oversight.

## 7. STUDY PROCEDURE

### 7.1 SCREENING

See section 6.5 Subject Recruitment, Informed Consent and Enrollment

### 7.2 REGISTRATION

After electronically signing the Informed Consent Form, the subject will be directed to the online registration page [REDACTED]. After registration is complete, the Pivot Study team will mail the sensor and email the subject the Baseline Questionnaire (age, gender, ethnicity, education, income, smoking history and behavior, use of smoking cessation medications, and attitudes and goals towards smoking) [REDACTED]

### **7.3 DAY 1 – DATE PAIRED DEVICE, GAVE FIRST BREATH SAMPLE AND COMPLETED BASELINE QUESTIONNAIRE**

Upon receipt of the sensor, the participant will self-train on how to use the study device using the available study Pivot Breath Sensor device labeling, including product packaging, Quick Start Guide, Package Insert, and a technical support line (phone number provided in packaging/Quick Start Guide) and online User Manual if needed. A member of the study staff or customer support may optionally call, text or email the participant to assist in device setup.

The participant will initiate using the product. Enrollment date (Day 1) will be defined as the first day the participant has completed all of the following: paired their breath sensor to the Sensor-Only app, taken their first breath sample using the Pivot Breath Sensor, and completed the Baseline Questionnaire.

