### Pivot Breath Sensor.

The primary endpoint will assess any change in the proportion of participants' Stage of Change response at day 28 compared to baseline

- A positive outcome is defined as a participant responding as more ready to quit. For example, a change in response from seriously thinking of quitting smoking "...within the next 6 months" at baseline to seriously thinking of quitting smoking "...within the next 30 days" at day 28.

The secondary endpoints include:

- The proportion of participants who reported  $\geq 1$  quit attempt by day 28; will be compared to zero
  - A quit attempt is defined as answering  $\geq 1$  to the following question: "Since you began using the Pivot Breath Sensor, how many times have you tried to quit smoking where you've gone at least 1 day without smoking a cigarette, even a single puff?"
- The proportion of participants who reduced their cigarettes per day (CPD) by  $\geq 50\%$  by day 28, compared to baseline

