**7.7 SCHEDULE OF STUDY ACTIVITIES**

Event	Screening 	Registration	1	7	14	21	28	56	84	84-98
Eligibility confirmed	X									
Phone call	X		X 							
Informed consent		X								
Receive breath sensor 			X							
Active use of breath sensor			X	X	X	X	X	X	X	
Survey		X		X	X	X	X	X	X	
- Baseline and demographic data		X								
- Access device settings				X	X	X	X	X	X	
- Feedback: breath sensor set-up				X						
- CPD		X		X	X	X	X	X	X	
- Desire to quit		X		X	X		X	X	X	
- Difficulty to stay quit		X		X	X		X	X	X	
- Stage of Change		X		X	X		X	X	X	
- Readiness to quit		X		X	X		X	X	X	
- Confidence to quit		X		X	X		X	X	X	
- Goals		X		X	X		X	X	X	
- Point prevalence abstinence					X	X	X	X	X	
- Quit attempts		X			X		X	X	X	
- CO reading understanding				X	X		X	X	X	
- Feedback: breath sensor experience and use				X	X		X	X	X	
- Feedback: impact of breath sensor				X	X	X	X			
- Feedback: commercialization					X		X			
Final questionnaire										X
Return breath sensor										X
Study completion										X

1 Screening is a phone call to prescreened candidates based on their responses to an online screening questionnaire.

2 Pivot Breath Sensor received by participant only after confirmation of eligibility and provision of electronic informed consent.

3 Optional phone call to assist with breath sensor set-up as needed

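### The enrolment rules let the Baseline Questionnaire be completed after sensor use has begun, although the schedule places it at Registration; it should be required before shipment

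*Combined protocol and SAP*

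**What the plan says.** The primary endpoint in section 6.3 is a comparison with baseline: "The primary endpoint will assess any change in the proportion of participants' Stage of Change response at day 28 compared to baseline". The cigarettes-per-day (CPD) endpoint in the same section also uses baseline. Section 10.2 treats participants as their own controls; there is no comparison group.

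Four places govern when baseline is taken:

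- **Section 7.2:** "After registration is complete, the Pivot Study team will mail the sensor and email the subject the Baseline Questionnaire". The questionnaire covers, among other items, "use of smoking cessation medications, and attitudes and goals towards smoking".
- **Section 7.3:** "Enrollment date (Day 1) will be defined as the first day the participant has completed all of the following": paired the sensor with the app, "taken their first breath sample using the Pivot Breath Sensor, and completed the Baseline Questionnaire". Section 6.4 lists the same tasks, plus consent, as the conditions for being enrolled.
- **Section 7.7, footnote 2:** "Pivot Breath Sensor received by participant only after confirmation of eligibility and provision of electronic informed consent".
- **Section 7.7, schedule:** the baseline survey, including Stage of Change and CPD, is marked under Registration. Receipt of the sensor is marked under Day 1, where no survey is marked.

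The quit-attempt item in section 6.3 has a different starting point. It begins "Since you began using the Pivot Breath Sensor, how many times have you tried to quit smoking".

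**The concern.** With no control group, the main comparison depends on the baseline answer being given before exposure to the device. Under the written rules a participant can receive the sensor, see CO values for some days, and only then answer the questionnaire that becomes the baseline. At the suggested minimum of 4 samples a day, a questionnaire answered a week after first use could follow 4 × 7 = 28 readings.

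Three endpoints are exposed. Where CO feedback acts early, part of the Stage of Change shift and part of the CPD reduction would already sit inside the baseline, so both changes would be understated. For quit attempts the direction reverses. Day 1 moves to the date of the late questionnaire while the question still counts from first sensor use, so the Day 28 answer covers more than 28 days. Section 6.6 sets that endpoint against an approximate monthly rate of 5%.

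**Working it through.** **Do the rules permit a late baseline?**

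1. Shipment does not wait for the questionnaire: section 7.2 puts both in one step, and footnote 2 of 7.7 names only eligibility and consent.
2. Day 1 and enrolment depend on all tasks being complete, not on their order (7.3, 6.4).
3. Pairing is not a barrier to exposure. Sections 5.1 and 5.3 show the CO value on the sensor's own screen and store it in the sensor's memory; storage in the app is additional, once paired.
4. A late baseline is not removed later. Section 9.1 asks for at least one breath sample and the questionnaire. The completer rule in 10.2 asks for a baseline response and an outcome response. Neither has a timing condition.
5. The 7.7 schedule points the other way, with baseline at Registration. The intention is visible, but the operative rules do not secure it.

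**Size.** The plan states no figure for this, so there is none to reproduce. The inputs from section 6.6 are 31% with increased Stage of Change (pilot, 14 days), 25% with at least one quit attempt, and a monthly benchmark of 5%. My assumptions are a share f = 10-40% of participants with a late baseline, a share g = 25-50% of their upward shifts already past by then, and a 7-day delay for the quit-attempt item.

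*Stage of Change.* Observed share = 31% × (1 − f × g).

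- f = 0.10, g = 0.25: 31% × 0.975 = 30.2%
- f = 0.40, g = 0.50: 31% × 0.80 = 24.8%

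*Quit attempts.* A 7-day delay gives a look-back of 35 days. At a constant rate, a late participant's probability is 1 − 0.75^(35/28) = 30.2%. Over the whole sample:

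- f = 0.10: 0.90 × 25% + 0.10 × 30.2% = 25.5%
- f = 0.40: 0.60 × 25% + 0.40 × 30.2% = 27.1%

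The benchmark over the same mix of look-backs uses 1 − 0.95^(35/28) = 6.2% for late participants:

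- f = 0.10: 0.90 × 5% + 0.10 × 6.2% = 5.1%
- f = 0.40: 0.60 × 5% + 0.40 × 6.2% = 5.5%

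*Power for the primary endpoint.* Section 6.6 names no test, so I used an exact two-sided McNemar test with 31% up and 3% down. At n = 185 power stays at 98% or more even if half of all upward shifts preceded baseline. The worst case above is 0.40 × 0.50 = 20%.

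*CPD.* The documents give nothing from which to size the effect on the CPD endpoint.

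**The case against.** The strongest reply is that the intended order is already clear. The schedule marks the baseline survey at Registration, section 7.2 describes it under that heading, and an email will normally arrive before a parcel. On this view section 7.3 only dates enrolment and does not move the questionnaire. Parts of 7.2 and of the recruitment material are also redacted, so participant instructions on order may exist unseen. This stands as far as intention goes: a reader might infer that the plan chose a post-exposure baseline, and the documents do not support that. But early arrival does not ensure early completion, and the Day 1 rule accommodates a questionnaire finished last.

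Second, the baseline is not the only pre-sensor information. Stage of Change and CPD are recruitment quotas applied around the screening call (6.3, 6.4), and CPD is an eligibility criterion, so earlier answers to both are implied. This also stands. They are not named as the endpoint baseline, but they can serve as a check.

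Third, a reader might infer that the opposing biases could never be disentangled. That goes too far. Sample time is recorded (10.1), and applying the Day 1 rule needs the questionnaire completion date, so late baselines could be identified if that time is kept. The plan does not expressly say it is. Identifying them would still not recover a missing pre-exposure answer.

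Fourth, the primary-endpoint bias is toward no change, if feedback works as the study hopes. That is fair: no false positive on the primary endpoint follows from this point.

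**Conclusion.** The point holds as a gap between the 7.7 schedule and the operative rules in 7.2, 7.3 and footnote 2. Those rules, with 9.1 and 10.2, admit a baseline taken after sensor use. Whether this happens, and how often, cannot be read from the documents.

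If 10-40% of participants were late, the effect would be modest: 31% seen as about 30.2% to 24.8%, and 25% quit attempts as about 25.5% to 27.1%. The direction for Stage of Change and CPD assumes that early CO feedback raises readiness or lowers smoking, which is the study's hope and not an established fact. A reader might take 30% quit attempts against a 6.2% benchmark as the expected distortion, but those values require every participant to be 7 days late. Nor does the point show a material loss of power for the primary endpoint. What is at stake is a clearly defined, pre-exposure baseline in a single-arm study. It should be changed because the remedy is simple and protects the main comparison.

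**What to change.** 1. Reconcile 7.2, 7.3 and footnote 2 of 7.7 with the schedule by requiring the Baseline Questionnaire to be submitted before the sensor is shipped. Holding back pairing instead would not be enough, because the sensor displays CO values itself.
2. Define Day 1 as the date of the first breath sample, so that the study clock and the quit-attempt question start together.
3. State that the questionnaire completion time is recorded.
4. In 10.2, repeat the primary and secondary analyses excluding anyone whose questionnaire is later than their first breath sample, and use the screening Stage of Change and CPD answers as a check on the baseline.

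The cost is a few sentences, one sensitivity analysis and a short shipping delay. People who never return the questionnaire would not receive a sensor, but under section 6.4 they would not count as enrolled anyway.
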